#### **Assessment of Intensity**

The investigator will make an assessment of intensity for each AE and SAE reported during the study and assign it to 1 of the following categories:

- Mild: Asymptomatic or mild symptoms; clinical or diagnostic observations only; intervention not indicated.
- Moderate: Minimal, local or noninvasive intervention indicated; limiting age-appropriate instrumental ADL. Instrumental ADL refers to preparing meals, shopping for groceries or clothes, using the telephone, managing money, etc.
- Severe: Severe or medically significant but not immediately life-threatening; hospitalization or prolongation of hospitalization indicated; disabling, limiting self care ADL. Self care ADL refers to bathing, dressing and undressing, feeding self, using the toilet, taking medications, and not bedridden.
- An event is defined as “serious” when it meets at least 1 of the predefined outcomes as described in the definition of an SAE, NOT when it is rated as severe.

#### **Assessment of Causality**

- The investigator is obligated to assess the relationship between study intervention and each occurrence of each AE or SAE. The investigator will use clinical judgment to determine the relationship.
- A “reasonable possibility” of a relationship conveys that there are facts, evidence, and/or arguments to suggest a causal relationship, rather than a relationship cannot be ruled out.
- Alternative causes, such as underlying disease(s), concomitant therapy, and other risk factors, as well as the temporal relationship of the event to study intervention administration, will be considered and investigated.

- The investigator will also consult the IB and/or product information, for marketed products, in his/her assessment.
- For each AE or SAE, the investigator **must** document in the medical notes that he/she has reviewed the AE or SAE and has provided an assessment of causality.
- There may be situations in which an SAE has occurred and the investigator has minimal information to include in the initial report to the sponsor. However, **it is very important that the investigator always make an assessment of causality for every event before the initial transmission of the SAE data to the sponsor.**
- The investigator may change his/her opinion of causality in light of follow-up information and send an SAE follow-up report with the updated causality assessment.
- The causality assessment is one of the criteria used when determining regulatory reporting requirements.
- If the investigator does not know whether or not the study intervention caused the event, then the event will be handled as “related to study intervention” for reporting purposes, as defined by the sponsor. In addition, if the investigator determines that an SAE is associated with study procedures, the investigator must record this causal relationship in the source documents and CRF, and report such an assessment in the dedicated section of the CT SAE Report Form and in accordance with the SAE reporting requirements.

Follow-Up of AEs and SAEs


• The investigator is obligated to perform or arrange for the conduct of supplemental measurements and/or evaluations, as medically indicated or as requested by the sponsor, to elucidate the nature and/or causality of the AE or SAE as fully as possible. This may include additional laboratory tests or investigations, histopathological examinations, or consultation with other healthcare providers.

• If a participant dies during participation in the study or during a recognized follow-up period, the investigator will provide Pfizer Safety with a copy of any postmortem findings, including histopathology.

• New or updated information will be recorded in the originally submitted documents.

• The investigator will submit any updated SAE data to the sponsor within 24 hours of receipt of the information.

#### 10.3.4. Reporting of SAEs

##### **SAE Reporting to Pfizer Safety via an Electronic Data Collection Tool**

- The primary mechanism for reporting an SAE to Pfizer Safety will be the electronic data collection tool.
- If the electronic system is unavailable, then the site will use the paper SAE data collection tool (see next section) to report the event within 24 hours.
- The site will enter the SAE data into the electronic system as soon as the data become available.
- After the study is completed at a given site, the electronic data collection tool will be taken off-line to prevent the entry of new data or changes to existing data.
- If a site receives a report of a new SAE from a study participant or receives updated data on a previously reported SAE after the electronic data collection tool has been taken off-line, then the site can report this information on a paper SAE form (see next section) or to Pfizer Safety by telephone.

##### **SAE Reporting to Pfizer Safety via CT SAE Report Form**

- Facsimile transmission of the CT SAE Report Form is the preferred method to transmit this information to Pfizer Safety.
- In circumstances when the facsimile is not working, notification by telephone is acceptable with a copy of the CT SAE Report Form sent by overnight mail or courier service.
- Initial notification via telephone does not replace the need for the investigator to complete and sign the CT SAE Report Form pages within the designated reporting time frames.

## **10.4. Appendix 4: Contraceptive and Barrier Guidance**

### **10.4.1. Male Participant Reproductive Inclusion Criteria**

Male participants are eligible to participate if they agree to the following requirements during the intervention period and for at least 28 days after the last dose of study intervention.

- Refrain from donating sperm.

PLUS either:

- Be abstinent from heterosexual intercourse with a female of childbearing potential as their preferred and usual lifestyle (abstinent on a long-term and persistent basis) and agree to remain abstinent.

OR

- Must agree to use a male condom when engaging in any activity that allows for passage of ejaculate to another person.

In addition to male condom use, a highly effective method of contraception may be considered in WOCBP partners of male participants (refer to the list of highly effective methods below in [Section 10.4.4](#)).

### **10.4.2. Female Participant Reproductive Inclusion Criteria**

A female participant is eligible to participate if she is not pregnant or breastfeeding and is not a WOCBP (see definitions below in [Section 10.4.3](#)).

### **10.4.3. Woman of Childbearing Potential**

A woman is considered fertile following menarche and until becoming postmenopausal unless permanently sterile (see below).

If fertility is unclear (eg, amenorrhea in adolescents or athletes) and a menstrual cycle cannot be confirmed before the first dose of study intervention, additional evaluation should be considered.

Women in the following categories are not considered WOCBP:

1. Premenopausal female with 1 of the following:
  - Documented hysterectomy;
  - Documented bilateral salpingectomy;
  - Documented bilateral oophorectomy.

For individuals with permanent infertility due to an alternate medical cause other than the above, (eg, mullerian agenesis, androgen insensitivity), investigator discretion should be applied to determining study entry.

Note: Documentation for any of the above categories can come from the site personnel's review of the participant's medical records, medical examination, or medical history interview. The method of documentation should be recorded in the participant's medical record for the study.

2. Postmenopausal female.

- A postmenopausal state is defined as no menses for 12 months without an alternative medical cause. In addition:
  - A high FSH level in the postmenopausal range must be used to confirm a postmenopausal state in women under 60 years old and not using hormonal contraception or HRT.
  - A female on HRT and whose menopausal status is in doubt will be required to use one of the nonestrogen hormonal highly effective contraception methods if they wish to continue their HRT during the study. Otherwise, they must discontinue HRT to allow confirmation of postmenopausal status before study enrollment.

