### 4.2.1. Population(s)

Participants enrolled in this study will be adults with inadequately controlled T2DM (as indicated by HbA1c at screening) on metformin monotherapy, which is considered first-line therapy for glycemic control according to current treatment guidelines. At screening, this study requires that participants with T2DM have been taking a minimum stable metformin dose of at least 500 mg/day for at least 2 months prior to the screening visit. The dose of metformin, where possible, is expected to remain the same until completion of study participation (ie, follow-up visit). Available in vitro data suggest that PF-07081532 is not expected to impact the PK of metformin via inhibition of OCT2, and the risk of a clinical interaction is deemed negligible. One or more cohorts of non-diabetic participants with obesity may be enrolled in this study. The safety, tolerability, PK and PD data collected in this study may be used to select doses and dosing scheme algorithms for future studies of PF-07081532.

The population planned for this study will be male and female adult participants. Female participants will be WONCBP, since at the present time embryofetal development toxicity studies with PF-07081532 have not been conducted. In male participants appropriate measures are expected to be followed to limit potential transfer of PF-07081532 in semen to partners (see [Appendix 4](#)).

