### Age and Sex:

1. Male and female participants must be between the ages of 18 and 70 years, inclusive, at the time of signing the ICD.
2. Females must be of non childbearing potential.
  - Refer to [Appendix 4](#) for reproductive criteria for males ([Section 10.4.1](#)) and females ([Section 10.4.2](#)) participants.

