### 5.3.4. Contraception

The investigator or his or her designee, in consultation with the male participant, will confirm that the participant has selected an appropriate method of contraception for the individual male participant and his partner(s) from the permitted list of contraception methods (see [Appendix 4](#)) and will confirm that the participant has been instructed in its consistent and correct use. At time points indicated in the [SoA](#), the investigator or designee will inform the male participant of the need to use effective contraception consistently and correctly and document the conversation and the male participant's affirmation in the participant's chart (participants need to affirm their consistent and correct use of at least 1 of the selected methods of contraception). In addition, the investigator or designee will instruct the participant to call immediately if the selected contraception method is discontinued or if pregnancy is known or suspected in the participant's female partner.

Female participants will not require use of contraception as they cannot be women of childbearing potential.

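### Section 10.4.3 lets a woman on HRT with unconfirmed menopausal status take part on contraception, which conflicts with Section 5.3.4 and the non-childbearing restriction, and no pregnancy test is scheduled

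*Protocol*

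**What the plan says.** Protocol Section 5.1, inclusion criterion 2, reads: "Females must be of non childbearing potential". It sends the reader to Appendix 4 for the detail. Section 10.4.2 repeats the rule and adds pregnancy status: "A female participant is eligible to participate if she is not pregnant or breastfeeding and is not a WOCBP". Section 4.2.1 gives the reason for the restriction: "since at the present time embryofetal development toxicity studies with PF-07081532 have not been conducted".

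Section 5.3.4 draws the consequence: "Female participants will not require use of contraception as they cannot be women of childbearing potential". The rest of that section describes choosing, instructing on and documenting contraception for male participants only.

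Section 10.4.3 starts from a default: "A woman is considered fertile following menarche and until becoming postmenopausal unless permanently sterile". It then lists the women who do not count as being of childbearing potential. Under the postmenopausal category, after a definition of 12 months without menses, come two further bullets:

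- The first concerns FSH. A high level "must be used to confirm a postmenopausal state in women under 60 years old and not using hormonal contraception or HRT".
- The second concerns women who take HRT and reads: "A female on HRT and whose menopausal status is in doubt will be required to use one of the nonestrogen hormonal highly effective contraception methods". This applies when she wishes to carry on with HRT during the study. The next sentence gives the other branch: "Otherwise, they must discontinue HRT to allow confirmation of postmenopausal status before study enrollment".

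Table 1 has an FSH test at Screening. It also has a row for reviewing contraception, marked at Screening and at several later time points, with no restriction by sex. Tables 1, 2 and 6 show no pregnancy test.

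**The concern.** Section 10.4.3 describes a woman whose menopausal status is, by its own words, unresolved, and gives her a way to take part with that status still unresolved. Section 5.3.4 rests on the premise that no such woman can be in the study. If the appendix is followed literally, a woman of unconfirmed status can be enrolled and dosed. The main body would then tell the site that she needs no contraception, and the schedule would contain no test for the pregnancy that Section 10.4.2 says must be absent.

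The restriction to women of non-childbearing potential exists because there are no embryofetal data for this compound. A gap in the text that implements it is therefore a safety matter, even if few women fall into it. Section 5 forbids eligibility waivers, so a site cannot settle the conflict by exemption. The point concerns eligibility and safety. It has no bearing on sample size, error rates or any planned analysis.

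**Working it through.** The plan gives no figure on this point. The check follows one woman through the text: she is on HRT, her menopausal status is in doubt, and she wishes to stay on HRT.

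1. **Eligibility chain.** Inclusion criterion 2 points to Section 10.4.2, which points to Section 10.4.3 for the definition. The answer therefore depends on Section 10.4.3.
2. **Her classification.** By default she is fertile until postmenopausal or permanently sterile. The HRT bullet sits within the postmenopausal category, so the layout counts her as not of childbearing potential, yet the bullet says her status is in doubt.
3. **Is her status resolved before entry?** The FSH requirement applies to women under 60 who use neither hormonal contraception nor HRT, so it does not reach her. Confirmation before enrolment is attached only to the branch in which HRT is stopped. On the branch in which HRT continues, nothing requires confirmation. A woman under 60 on hormonal contraception is also outside the FSH rule.
4. **Contraception.** Section 10.4.3 requires it of her. Section 5.3.4 says no female participant needs it. Both cannot hold for the same participant.
5. **Scheduled tests.** Pregnancy tests visible in Tables 1, 2 and 6: 0. FSH is the only female reproductive test. Table 1 has a redacted entry that cannot be read, but Table 6, the list of required safety laboratory tests, shows none.
6. **Contraception review.** The Table 1 row is not limited by sex, so a review may be made for women. The only text that explains it, Section 5.3.4, is written for men. What is to be reviewed for a woman is not stated.
7. **Window of risk.** Participants are admitted on Day -7 and stay until at least Day 45: 7 + 45 = 52 days, which matches the 52 inpatient days in Section 4.1. All 42 doses (Days 1 to 42) fall inside that stay. Two periods lie outside it:
   - *Before admission.* Screening may be up to 28 days before randomization, and no pregnancy test is listed at Screening or at admission.
   - *After discharge.* The last contact is 28 to 35 days after the last dose, that is Day 42 + 28 = 70 to Day 42 + 35 = 77. With discharge on Day 45, this leaves 70 - 45 = 25 to 77 - 45 = 32 days. Section 10.4.1 sets a contraception period for men of at least 28 days after the last dose. No matching period is stated for her.
8. **Number affected.** Planned enrolment is 3 × 12 = 36, of whom 3 × 9 = 27 receive active drug. With all three optional cohorts it is 6 × 12 = 72, of whom 6 × 9 = 54 receive active drug. These are totals for both sexes. The documents give no count of women, of HRT users or of doubtful status, so they are only ceilings.

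**The case against.** The strongest reply is that the female criteria form one chain. Inclusion criterion 2 defers to Appendix 4, and the HRT bullet stands under the heading for women not of childbearing potential, after the 12-month definition. On that layout she has already gone a year without menses, and she is asked to use highly effective contraception as a further precaution. Section 10.4.3 also suggests considering further evaluation when fertility is unclear and a menstrual cycle cannot be confirmed before the first dose. Section 8.3.5.1 requires a pregnancy found in a female participant to be reported. Dosing is entirely inpatient.

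Much of this stands, and it rules out three stronger readings that a reader might infer:

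- *That sites would reach opposite eligibility answers.* Because criterion 2 refers to Appendix 4, the documents do not set up two cleanly competing rules. The direct clash is over contraception, together with a classification that does not resolve her status.
- *That no contraception check is scheduled for women.* The Table 1 row is not limited to men. What is missing is any explanation of how it applies to women.
- *That she is wholly unprotected.* The bullet itself requires contraception, and Section 10.4.2 requires that she is not pregnant.

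The reply does not remove the conflict. The bullet still treats her status as doubtful after the 12-month definition. The further evaluation is only to be considered. Reporting a pregnancy depends on finding one, and no scheduled test would do so.

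**Conclusion.** The inconsistency is real and should be corrected. Section 10.4.3 permits participation with unconfirmed menopausal status and requires contraception. Section 5.3.4 denies that any female participant needs it, on a premise that Section 10.4.3 breaks. Section 10.4.2 requires absence of pregnancy, and no visible scheduled test verifies it.

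The size is limited. The number of women is not given and is probably small. A reader might take the 42 daily doses as 42 days of opportunity to conceive; the documents do not support that, because every dose is given during confinement. What remains is mainly a pregnancy already present but undetected at entry, and the weeks after discharge.

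This rests on two assumptions: that the redacted Table 1 entry is not a pregnancy test, which Table 6 supports, and that Section 5.3.4 is the only text explaining the contraception row. A reader might also infer that one of the two HRT branches is the correct one. The documents do not settle that, and it is a clinical decision for the sponsor.

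**What to change.** The sponsor should reconcile Sections 4.2.1, 5.1 (criterion 2), 5.3.4, 10.4.2 and 10.4.3 with Tables 1 and 2 and Table 6. After the change, three things should agree for a woman on HRT or hormonal contraception whose menopausal status is unconfirmed:

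- whether she is eligible;
- whether contraception is required of her;
- which checks are scheduled, including how the Table 1 contraception row applies to women and how the not-pregnant condition in Section 10.4.2 is to be verified.

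No particular clinical rule is proposed. The cost is a short text amendment. Depending on how the sponsor resolves it, the eligibility of a few women, or the checks made on them, may change.

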#### **10.4.4. Contraception Methods**

Contraceptive use by men or women should be consistent with local availability/regulations regarding the use of contraceptive methods for those participating in clinical trials.

##### **Highly Effective Methods That Have Low User Dependency**

1. Implantable progestogen-only hormone contraception associated with inhibition of ovulation.
2. Intrauterine device.
3. Intrauterine hormone-releasing system.
4. Bilateral tubal occlusion (eg, bilateral tubal ligation).
5. Vasectomized partner.
  - A vasectomized partner is a highly effective contraceptive method provided that the partner is the sole sexual partner of the WOCBP and the absence of sperm has been confirmed. If not, an additional highly effective method of contraception should be used. The spermatogenesis cycle is approximately 90 days.

### **Highly Effective Methods That Are User Dependent**

1. Combined (estrogen- and progestogen-containing) hormonal contraception associated with inhibition of ovulation:
  - Oral;
  - Intravaginal;
  - Transdermal;
2. Progestogen-only hormone contraception associated with inhibition of ovulation:
  - Oral;
  - Injectable.
3. Sexual abstinence:
  - Sexual abstinence is considered a highly effective method only if defined as refraining from heterosexual intercourse during the entire period of risk associated with the study intervention. The reliability of sexual abstinence needs to be evaluated in relation to the duration of the study and the preferred and usual lifestyle of the participant.

One of the following effective barrier methods must be used in addition to the highly effective methods listed above that are user dependent:

- Male or female condom with or without spermicide;
- Cervical cap, diaphragm, or sponge with spermicide;
- A combination of male condom with either cervical cap, diaphragm, or sponge with spermicide (double-barrier methods).

CCI [REDACTED]  
[REDACTED]

- | [REDACTED]
- | [REDACTED]
- | [REDACTED]
- | [REDACTED]
- | [REDACTED]
- | [REDACTED]
- | [REDACTED]
- | [REDACTED]
- | [REDACTED]
- | [REDACTED]

## 10.6. Appendix 6: Liver Safety: Suggested Actions and Follow-Up Assessments

### Potential Cases of Drug-Induced Liver Injury

Humans exposed to a drug who show no sign of liver injury (as determined by elevations in transaminases) are termed “tolerators,” while those who show transient liver injury but adapt are termed “adaptors.” In some participants, transaminase elevations are a harbinger of a more serious potential outcome. These participants fail to adapt and therefore are “susceptible” to progressive and serious liver injury, commonly referred to as DILI. Participants who experience a transaminase elevation above  $3 \times \text{ULN}$  should be monitored more frequently to determine if they are “adaptors” or are “susceptible.”

In the majority of DILI cases, elevations in AST and/or ALT precede TBili elevations ( $>2 \times \text{ULN}$ ) by several days or weeks. The increase in TBili typically occurs while AST/ALT is/are still elevated above  $3 \times \text{ULN}$  (ie, AST/ALT and TBili values will be elevated within the same laboratory sample). In rare instances, by the time TBili elevations are detected, AST/ALT values might have decreased. This occurrence is still regarded as a potential DILI. Therefore, abnormal elevations in either AST OR ALT in addition to TBili that meet the criteria outlined below are considered potential DILI (assessed per Hy’s law criteria) cases and should always be considered important medical events, even before all other possible causes of liver injury have been excluded.

The threshold of laboratory abnormalities for a potential DILI case depends on the participant’s individual baseline values and underlying conditions. Participants who present with the following laboratory abnormalities should be evaluated further as potential DILI (Hy’s law) cases to definitively determine the etiology of the abnormal laboratory values:

- Participants with AST/ALT and TBili baseline values within the normal range who subsequently present with AST OR ALT values  $>3 \times \text{ULN}$  AND a TBili value  $>2 \times \text{ULN}$  with no evidence of hemolysis and an alkaline phosphatase value  $<2 \times \text{ULN}$  or not available.
- For participants with baseline AST **OR** ALT **OR** TBili values above the ULN, the following threshold values are used in the definition mentioned above, as needed, depending on which values are above the ULN at baseline:
  - Preexisting AST or ALT baseline values above the normal range: AST or ALT values  $>2$  times the baseline values AND  $>3 \times \text{ULN}$ ; or  $>8 \times \text{ULN}$  (whichever is smaller).
  - Preexisting values of TBili above the normal range: TBili level increased from baseline value by an amount of at least  $1 \times \text{ULN}$  **or** if the value reaches  $>3 \times \text{ULN}$  (whichever is smaller).

Rises in AST/ALT and TBili separated by more than a few weeks should be assessed individually based on clinical judgment; any case where uncertainty remains as to whether it represents a potential Hy’s law case should be reviewed with the sponsor.

The participant should return to the investigator site and be evaluated as soon as possible, preferably within 48 hours from awareness of the abnormal results. This evaluation should include laboratory tests, detailed history, and physical assessment.

In addition to repeating measurements of AST and ALT and TBili for suspected Hy's law cases, additional laboratory tests should include albumin, CK, direct and indirect bilirubin, GGT, PT/INR, total bile acids, and alkaline phosphatase. Consideration should also be given to drawing a separate tube of clotted blood and an anticoagulated tube of blood for further testing, as needed, for further contemporaneous analyses at the time of the recognized initial abnormalities to determine etiology. A detailed history, including relevant information, such as review of ethanol, acetaminophen/paracetamol (either by itself or as a coformulated product in prescription or over-the-counter medications), recreational drug, or supplement (herbal) use and consumption, family history, sexual history, travel history, history of contact with a jaundiced person, surgery, blood transfusion, history of liver or allergic disease, and potential occupational exposure to chemicals, should be collected. Further testing for acute hepatitis A, B, C, D, and E infection, liver imaging (eg, biliary tract), and collection of serum samples for acetaminophen/paracetamol drug and/or protein adduct levels may be warranted.

All cases demonstrated on repeat testing as meeting the laboratory criteria of AST/ALT and TBili elevation defined above should be considered potential DILI (Hy's law) cases if no other reason for the LFT abnormalities has yet been found. **Such potential DILI (Hy's law) cases are to be reported as SAEs, irrespective of availability of all the results of the investigations performed to determine etiology of the LFT abnormalities.**

A potential DILI (Hy's law) case becomes a confirmed case only after all results of reasonable investigations have been received and have excluded an alternative etiology.

